8 CHANGES FROM PROTOCOL-SPECIFIED ANALYSES

Because both studies will be terminated early and for the purpose of abbreviated CSR originally planned evaluations that will not be performed include:

Additional analysis of Secondary Efficacy Endpoints:

- Longitudinal analysis using a mixed model of the change from baseline in continuous outcomes measured at multiple post-baseline time points.
- Determination whether the declaration of response based on the co-primary endpoints for induction parallels the pattern of CDAI scores
- Comparison of changes in the CDAI scores between responders and non-responders to the co-primary endpoints via Wilcoxon rank-sum test

Analysis Exploratory Endpoints:

- Characterization of stool microbiota at baseline and after 16 and 52 weeks of treatment.
 - Baseline and post-treatment bacterial DNA isolated from stool for 16S rRNA gene amplification.
 - Descriptive characterization of bacteria in stool by:
 - Isolation and identification of selected Gramnegative and Gram-positive bacteria.
 - Resistance to selected antibiotics, including rifaximin and rifampin.
- Genomic profiling of pregnane X receptor (PXR) in blood.
- Population pharmacokinetics of rifaximin.

Clinical Laboratory Assessments:

- A summary of shifts from baseline to final evaluation for each treatment group for each parameter.

Electrocardiogram

- QT correction based on linear regression techniques

These changes will be documented in the Clinical Study Report

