### 8.2 Determination of Sample Size

The information below provides the background information for sample size determination for the induction of clinical remission with endoscopic response at 16 weeks followed by clinical and endoscopic remission at 52 weeks. For placebo, the expected rates are based on data from a Phase 2 study (RETIC 03/06) conducted in subjects with active moderate Crohn's disease. The rates for Rifaximin DR are based on the assumption that Rifaximin DR will provide a somewhat higher induction of remission rate.

Expected rates for induction of clinical remission with endoscopic response at Week 16 are 40% for placebo and 55% for Rifaximin DR.

Based on a significance level of 5% (alpha 0.05), a sample size of approximately 240 subjects per treatment group will have at least 90% power to test the hypothesis that Rifaximin DR is superior to placebo for each co-primary endpoint considered individually. Approximately 80% power is available to detect significant differences between Rifaximin DR and placebo for both co-primary endpoints.

For the Long Term Treatment Phase, a 15% treatment effect is expected for both clinical symptom and endoscopic remission at Week 52. Based on this assumption and testing at a significance level of 5% (alpha 0.05), a sample size of approximately 210 subjects per treatment group will have at least 90% power to test the key secondary efficacy hypothesis that Rifaximin DR is superior to placebo when each key co-secondary endpoint is considered individually. In addition, approximately 80% power is available to detect significant differences between Rifaximin DR and placebo for each of the key co-secondary endpoints.

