Time to event data (for example, time to clinical remission) will be analyzed by Kaplan-Meier analysis (PROC LIEFTTEST in SAS/STAT) stratified by country. Additionally, the change from baseline in continuous outcomes measured at multiple post-baseline time points will be analyzed longitudinally using a mixed model. Models will include fixed effects for baseline

Confidential

---

value, country, treatment, week and the treatment by week interaction and allow for random subject effects. Treatment and week will each be fit as categorical variables. Models will be fit using SAS Proc Mixed assuming a compound symmetric correlation structure allowing for heterogeneous variances by week. The Kenward-Rogers approach for computing denominator degrees of freedom will be used to account appropriately for pooling of within- and between-subject variance estimates. Least squares means with 95% confidence intervals will be presented for each treatment\*week cross-classification. The basic SAS code will follow the structure below:

```
proc mixed;
class treatment country week subjectID;
model Y = baseline country treatment week treatment*week/ddfm=KenwardRoger solution;
random int/ subject=subjectID type =VC;
lsmeans treatment*week/stderr;
run;
```

Estimate and contrast statements will be included to compare the mean change from baseline averaged over all weeks for the treatment comparison.

To determine whether the declaration of response based on the co-primary endpoints for induction parallels the pattern of CDAI scores, Spearman correlation analyses will be applied to CDAI scores with the occurrence or non-occurrence of response based on the co-primary endpoints (Yes or No). Wilcoxon rank-sum test will be conducted to compare changes in the CDAI scores between responders and non-responders to the co-primary endpoints.

The Work Productivity and Activity Impairment Questionnaire: Crohn's disease (WPAI: CD) is an instrument with 6 questions that will be used to assess the effect of CD on subjects' work habits. A copy of the WPAI: CD questionnaire is provided in Appendix 6.

WPAI: CD outcomes are expressed as impairment percentages, with higher numbers indicating greater impairment and less productivity, i.e., worse outcomes. The four WPAI: CD outcome scores are computed as follows:

- % work time missed due to CD =  $100 * Q2 / (Q2 + Q4)$
- % impairment while working due to CD =  $100 * Q5 / 10$

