7.2 Randomization and Unblinding

Subjects who successfully complete the Screening Period will enter the Treatment Period and will be randomized in a 1:1 allocation to one of two treatment groups for the duration of the study as assigned by the means of centralized electronic randomization system. Randomization will be stratified by study center within a country.

Only in the case of an emergency, when knowledge of the study drug is essential for the clinical management or welfare of the subject, will the investigator be allowed to unblind a subject's treatment assignment. If the investigator breaks the blind for an individual subject, the reason must be recorded on the CRF and the subject will be removed from the study.

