7.3 Sample Size

For sample size justification, reference corresponding study protocols.

Originally planned sample sizes per arm for each of the studies are listed below:

Study	Treatment A: Rifaximin DR Tablets 800 mg BID	Treatment B: Placebo BID
RECD3125	330	330
RECD3126	330	330

Both studies will be terminated early therefore the actual sample size may vary.

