7.7.1 Primary Efficacy Analysis

7.7.1.1 Induction Phase

There will be two co-primary measures of efficacy assessed during the Induction Phase. The first co-primary endpoint is:

- Clinical symptom remission defined by (1) the total number of liquid/very soft stools for the 7 days prior to the Week 16 visit being ≤ 10 (from CDAI Item 1); AND (2) an

abdominal pain rating of ≤ 1 (from CDAI Item 2) on each day for the 7 days prior to the Week 16 visit.

The second co-primary endpoint is:

- Endoscopic response defined as a ≥ 3 -point decrease in the SES-CD from baseline to the SES-CD score obtained between Week 16 and Week 17. SES-CD scores will be calculated from centrally-read digital video of ileocolonoscopies performed at baseline and between Week 16 and Week 17.

For each endpoint, the null hypothesis $H_0: \pi_R - \pi_P = 0$ versus the alternative $H_A: \pi_R - \pi_P \neq 0$ is of interest, where π_R is the binomial parameter for induction of remission/response for the Rifaximin DR group, and π_P is the binomial parameter for induction of remission/response for the placebo group. Subjects who require the initiation of rescue medication and/or surgery for CD will be considered treatment failures from the date of the introduction of the rescue medication and/or surgery, regardless of their actual response data. The Cochran-Mantel-Haenszel (CMH) test, stratified by country, will be used to test the hypothesis. Each null hypothesis of no difference will be rejected if the resulting p-value for the respective statistical test is less than 0.05. Significance for the induction claim will only be declared if both null hypotheses are rejected. As such, the overall Type I error rate will be maintained at the 5% level without adjustment for multiple comparisons.

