7.7.2.3 Continuous outcomes

Change from baseline for the continuous outcomes include:

- Change from baseline in SES-CD score at Week 16 and Week 52.
- Change from baseline in indices of health outcomes (Inflammatory Bowel Disease Questionnaire [IBDQ], Work Productivity and Activity Impairment Questionnaire for Crohn's Disease [WPAI-CD]) at post-baseline time points.
- Change from baseline in markers of inflammation (e.g. CRP, interleukins, cytokines, fecal calprotectin) at post-baseline time points.

Change from baseline in continuous outcomes will be analyzed by fitting fixed effects linear models to the data. An initial model with terms for treatment, country, baseline, and baseline by treatment interaction will be fitted. The interaction term will be tested at a 0.10 level. A non-significant interaction will result in dropping the term from the model in subsequent analyses. If the final model involves heterogeneous slopes, then the analysis will include overall plots of baseline versus change from baseline by treatment groups, and plots of the estimated regression lines.

Treatment differences will be estimated and tested at 25th, 50th and 75th percentiles of the baseline value.

The Work Productivity and Activity Impairment Questionnaire: Crohn's disease (WPAI: CD) is an instrument with 6 questions that will be used to assess the effect of CD on subjects' work habits.

WPAI: CD outcomes are expressed as impairment percentages, with higher numbers indicating greater impairment and less productivity, i.e., worse outcomes. The four WPAI: CD outcome scores are computed as follows:

- % work time missed due to CD = $100 \times Q2 / (Q2 + Q4)$
- % impairment while working due to CD = $100 \times Q5 / 10$
- % overall work impairment = $100 \times [Q2 / (Q2 + Q4) + (1 - Q2 / (Q2 + Q4)) \times (Q5 / 10)]$

- % activity impairment due to CD = $100 * Q6/10$

The IBDQ Global Score is the sum of 32 responses, each ranging from 1 to 7, thus the Global Score ranges from 32 to 224; a higher score indicating a better quality of life.

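### Dropping the additional mixed model leaves the Week 52 continuous secondaries on available-case linear models with no missing-data method, in studies that are to stop early

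*SAP*

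**What the plan says.** Protocol 8.6.2 gives two analyses for continuous change from baseline. The first is a linear model with treatment, country, baseline and baseline-by-treatment terms. The second, introduced as additional, is a mixed model over all post-baseline visits with treatment, week and treatment-by-week effects, for which SAS code is printed.

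The SAP keeps the first. Section 7.7.2.3 states: "Change from baseline in continuous outcomes will be analyzed by fitting fixed effects linear models to the data". That model has no week term and no within-subject structure. Section 8 drops the second, listing "Longitudinal analysis using a mixed model of the change from baseline in continuous outcomes measured at multiple post-baseline time points" among the evaluations that will not be performed. The reasons given are early termination and an abbreviated study report. Section 7.3 says: "Both studies will be terminated early therefore the actual sample size may vary".

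The Worst-Case rule and the sensitivity analyses in SAP 7.10.1 and 7.10.2 apply to the primary and key secondary endpoints, all of which are binary. SAP 7.1 has a general sentence against imputing missing values, but it follows a sentence on safety data. Nothing else addresses missing continuous secondaries.

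**The concern.** The outcomes are measured repeatedly: SES-CD and inflammation markers at Weeks 16 and 52, and IBDQ and WPAI-CD at Weeks 16, 28, 40 and 52. Stopping the studies early can be expected to leave more subjects with the earlier values but no Week 52 value. These are the subjects whose data the mixed model would use for the Week 52 comparison and the visit-wise model cannot. The reason given for dropping the model is therefore also a reason to keep it.

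Two things are at stake at Week 52. One is precision. The other is validity if leaving depends on results already observed, because a likelihood model is valid under missing-at-random while a comparison of those still observed in general is not. The SAP states no assumption for these outcomes and plans no sensitivity analysis or count of missing values.

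**Working it through.** **The plan's own figure.** The documents give no SD, effect size or power for any continuous secondary. The nearest stated figure is for the co-primaries: "Expected rates for induction of clinical remission with endoscopic response at Week 16 are 40% for placebo and 55% for Rifaximin DR", and "a sample size of approximately 240 subjects per treatment group will have at least 90% power". With two-sided alpha 0.05 and 1:1 allocation:

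- Power = Φ{[0.15·√240 − 1.96·√(2 × 0.475 × 0.525)] / √(0.40 × 0.60 + 0.55 × 0.45)} = Φ{(2.324 − 1.384)/0.698} = Φ(1.346) = 91.1%.

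The stated figure is reproduced, but it says nothing about the continuous outcomes.

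**Inputs for the check.** From the documents: 330 per arm as planned (Protocol 8.2), and a Week 16 value preceding the Week 52 value. Assumed, because the documents do not give them: SD 1; true effect −0.300 at both visits (negative is benefit); correlation 0.3 of each visit with baseline; Week 16 to Week 52 correlation ρ of 0.5 or 0.7; 20%, 40% or 60% missing at Week 52. The available-case linear model, adjusted for baseline, is compared with a two-visit likelihood estimate that also uses every Week 16 value. The latter stands in for the mixed model.

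**Precision when missingness is unrelated to outcome.** Let r be the Week 16 to Week 52 correlation given baseline and f the fraction observed at Week 52.

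- r = (ρ − 0.3²)/(1 − 0.3²): 0.41/0.91 = 0.451 for ρ = 0.5, and 0.61/0.91 = 0.670 for ρ = 0.7.
- Available-case SE = √[2 × 0.91/(330f)].
- Likelihood SE = available-case SE × √[1 − r²(1 − f)].
- 40% missing, ρ = 0.5: √(1.82/198) = 0.096; × √(1 − 0.203 × 0.4) gives 0.092.
- 60% missing, ρ = 0.7: √(1.82/132) = 0.117; × √(1 − 0.449 × 0.6) gives 0.100.

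Simulation with 1,500 replicates gives 0.095 against 0.091, and 0.118 against 0.101. The available-case SE is thus larger by 0.095/0.091 = 1.04 and 0.118/0.101 = 1.17, about 4% and 17%. In the formula this ratio depends only on r and f, so it does not change if early termination makes the arms smaller than 330.

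**Bias under different reasons for missing Week 52 values** (true effect −0.300; ranges over 20–60% missing and both correlations):

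| Mechanism | Available-case estimate |
|---|---|
| Unrelated to outcome, as in a purely administrative stop | −0.298 to −0.303 |
| Poor Week 16 responders leave, both arms | −0.274 to −0.243 |
| Placebo leave when doing badly, active when doing well | −0.111 to +0.502 |
| The opposite pattern by arm | −0.489 to −1.101 |

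The likelihood estimate lies between −0.295 and −0.304 throughout. In every scenario missingness depends at most on arm and the Week 16 value, which is the condition under which the method is valid. Where departure patterns differ by arm, it is not always the more precise estimate (60% missing, ρ = 0.5, third row: SE 0.133 against 0.114); its advantage there is freedom from bias.

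**The printed code.** Protocol 8.6.2 describes compound symmetry with variances that differ by week. The code has "random int/ subject=subjectID type =VC" and no REPEATED statement, which fits equal variances at all weeks. It should not be reused unchanged.

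**The case against.** - **The main analysis survives.** The linear model is listed first in the protocol and stays in the SAP; what was removed was additional, and the removal is disclosed with reasons. This stands. It argues for restoring the mixed model beside the linear model, not in its place.
- **The direction of bias is unknown.** A reader might infer that the change shrinks the treatment effect. The documents do not support that: they give no dropout rate, mechanism or arm pattern. An administrative stop produces no bias, and other mechanisms can push the estimate either way.
- **Earlier data are still used.** A reader might infer that the Week 16 to 40 data are thrown away. They are not: SES-CD is analysed at Week 16, and the other outcomes at post-baseline time points. Only the Week 52 estimate fails to draw on them. For SES-CD and the markers there is just one earlier post-baseline visit to draw on.
- **Available-case analysis is inferred.** Protocol 4.5 asks for End of Treatment assessments at premature withdrawal, including ileocolonoscopy, and sponsor termination is a listed reason. Some subjects may therefore have a late value, but neither document says to which visit it would be assigned. This leaves the amount of missing Week 52 data uncertain; it does not supply a method.
- **The stakes are bounded.** Under SAP 7.7.2.4, all secondary endpoints become descriptive if the co-primaries are not significant. This stands and lowers the weight of the point, but the SAP plans inference otherwise.

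**Conclusion.** The point holds as a modest, inexpensive improvement. The Week 52 continuous secondaries are left on models that are in effect available-case, with no missing-data method. If missingness is unrelated to outcome, the loss is precision alone: about 4% on the standard error at 40% missing and correlation 0.5, and about 17% at 60% missing and correlation 0.7. If missingness depends on earlier outcomes, bias is possible, but neither its direction nor its size can be read from the documents. All these sizes rest on assumed correlations, missing fractions and dropout mechanisms, and show a range only. The likelihood model's protection itself rests on missing-at-random; if leaving depends on unobserved Week 52 values, neither analysis is protected.

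**What to change.** Delete this bullet from SAP Section 8. In SAP 7.7.2.3, restore the longitudinal model for every continuous secondary with two or more post-baseline visits, alongside the existing linear model and its baseline-by-treatment test:

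- fixed effects for baseline, country, treatment, week and treatment-by-week;
- REPEATED week / SUBJECT=subjectID TYPE=UN, with CSH as the fallback, replacing the printed RANDOM statement;
- Kenward-Roger degrees of freedom;
- treatment contrasts at Week 16 and Week 52.

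State the missing-at-random assumption. Tabulate missing Week 52 values by arm and reason, with sponsor termination as its own category, and say how an early End of Treatment value is assigned to a visit, since the table depends on it. Keep the rule that results are descriptive if the co-primaries are not significant.

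The cost is about one PROC MIXED call per outcome, most of it already written in the protocol, one table, and a slightly longer abbreviated report.
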